3.4.3 Presentation of results

Uncorrected QT interval will only be listed.

Continuous ECG parameters will be summarised by means of descriptive statistics at each analysis visit. Actual values and changes from baseline will be tabulated separately.

Abnormalities of the actual values will be presented as cross-tabulations of the abnormality at each post-baseline analysis visit, and at the worst-case analysis visit versus the baseline abnormality. Numbers and cumulative numbers (QTcF only) of subjects with treatment-emergent abnormalities will also be shown.

Abnormalities of the QTcF changes will be presented as tabulations of the change abnormality at each post-baseline analysis visit and at the worst-case analysis visit. Cumulative numbers of subjects with change abnormalities will also be shown.

All ECG data will be listed, but only for subjects with any post-baseline abnormality or clinical significant value or change.

3.5 LUNG FUNCTION

3.5.1 Available data

The following lung function parameters will be collected during the challenge period: FEV1 (L), FEV1 as % of predicted, FEV1/FVC ratio, FEV1/FVC ratio (%), FVC (L) and FVC as % of predicted.

3.5.2 Derivation rules

Not applicable

3.5.3 Presentation of results

FEV1 as % of predicted and FVC as % of predicted will be summarised by means of descriptive statistics at each analysis visit. Actual values and changes from baseline will be tabulated separately.

All lung function data will be listed.

3.6 PHYSICAL EXAMINATIONS

Abnormal physical examination findings will be listed.

	Statistical Analysis Plan	
FLU010	Final analysis	Final 3.0 of 15JUN2020

4. GENERAL CHARACTERISTICS ANALYSES

4.1 SUBJECT DISPOSITION

The following subject data will be tabulated:

- The number of subjects in each analysis set
- Dates of first signed informed consent, last visit and last contact (overall only)
- The number and percentage of subjects who completed or discontinued the study and the number and percentage of subjects for each study discontinuation reason by phase (vaccination / challenge)

All information collected in the CRF concerning allocation, code breaking and study discontinuation and information on phases will be listed.

4.2 PROTOCOL DEVIATIONS AND ELIGIBILITY

The number and percentage of subjects with major protocol deviations will be tabulated, overall and per class of deviation.

All available information concerning major protocol deviations, violations on eligibility criteria and subjects not treated will be listed.

4.3 DEMOGRAPHIC AND OTHER BASELINE CHARACTERISTICS

4.3.1 *Available data*

The following parameters will be available:

- Demographics: sex, race, height, weight at screening, date of birth, date of signing informed consent form (ICF),
- Tobacco history and smoking status
- Screening tests: serology, alcohol breath test and urine drug screen, pregnancy tests

4.3.2 *Derivation rules*

The following parameters will be derived:

- Age = (date of ICF - date of birth)/365.25
Note: Age will be rounded as detailed in section 5.3.4.
- Body mass index (BMI) at screening (kg/m^2) = (weight at screening (kg)) / (height at screening (m))²

Note: Screening is defined in section 5.2.4. The BMI will be recalculated and rounded as detailed in section 5.3.4, even when already available in the database.

4.3.3 *Presentation of results*

Demographics will be presented using descriptive statistics for age, height, weight and BMI and frequency tabulations for sex, race and smoking status.

	Statistical Analysis Plan	
FLU010	Final analysis	Final 3.0 of 15JUN2020

All demographic data will be listed. Listings will also be created for tobacco history, serology, alcohol breath test and urine drug screen and pregnancy tests.

4.4 MEDICAL HISTORY AND CONCOMITANT DISEASES

4.4.1 *Available data*

For each medical history and concomitant disease finding, a start and stop date or ongoing flag is collected.

4.4.2 *Derivation rules*

The following parameters will be derived:

- Medical history finding: not ongoing at the screening visit
- Concomitant disease finding: still ongoing at the screening visit

4.4.3 *Presentation of results*

All medical history and concomitant diseases data will be listed separately.

4.5 PRIOR AND CONCOMITANT THERAPIES

4.5.1 *Available data*

All therapies are coded using WHODrug. No ATC selection is performed. For each therapy, a start date or prior flag and stop date or ongoing flag are collected.

4.5.2 *Derivation rules*

Based on their start and stop date(time), prior and concomitant therapies will be allocated to each phase and period during which they were administered. A therapy can therefore be reported in more than one phase or period.

Phases and periods are defined in section 5.2.1. Therapies with (partially) missing dates will be allocated to each phase / period unless the available parts of the therapy start or stop date(time) provide evidence the therapy was not taken during that phase / period.

4.5.3 *Presentation of results*

All prior and concomitant therapies data will be listed.

4.6 EXPOSURE TO STUDY DRUG AND TREATMENT COMPLIANCE

4.6.1 *Available data*

Vaccination occurs in 7 cohorts, with an approximate 3-week interval. Subjects are vaccinated only once, but for each cohort, vaccination can occur on multiple scheduled dates. Challenge occurs at least 6 weeks later, in 8 cohorts, with a 3-week interval. In case the challenge cohort is different from the vaccination cohort, this is documented in a structured comment in the clinical database.

4.6.2 *Derivation rules*

Time between vaccination and challenge will be calculated in days as date of challenge - date of vaccination + 1

	Statistical Analysis Plan	
FLU010	Final analysis	Final 3.0 of 15JUN2020

4.6.3 Presentation of results

The number and percentage of subjects who were vaccinated will be shown, both total and by vaccination cohort. A similar table will be prepared for the challenge. Time between vaccination and challenge will be be presented using descriptive statistics.

More details can be found in the list of tables and listings (see section 8)

	Statistical Analysis Plan	
FLU010	Final analysis	Final 3.0 of 15JUN2020

5. GENERAL METHODOLOGY

5.1 ANALYSIS SETS

5.1.1 *Analysis sets*

The following analysis sets will be considered in the statistical analysis:

All randomised subjects subjects who were *randomised* into this study set (RND):

Safety analysis set (SAF) subjects who were *exposed* to the vaccine, according to the vaccine actually received

Intent-to-treat set (ITT) randomised subjects who received the challenge inoculation, according to randomised treatment group

Per-protocol set (PP) ITT subjects without any major protocol deviations impacting the primary endpoint and *remain in the quarantine facility for the full extent of the challenge phase*

Challenge safety set (CSAF) randomised subjects who received the challenge inoculation, according to actual treatment received

Programming notes:

- Randomised is defined as having a complete randomisation date in the database or any information to confirm randomisation.
- Being exposed to the vaccine is defined as having a complete exposure date in the database or any information to confirm vaccination.
- If a subject does not remain in the quarantine facility for the full extent of the challenge phase, this will be reported as a major protocol deviation.
- Major protocol deviations impacting the primary endpoint will be flagged as such in the database.

Unless stated otherwise, the ITT will be used for the efficacy and immunogenicity tables, listings and figures. The SAF will be used for the safety and general characteristics tables, listings and figures. The primary efficacy analysis will be repeated on the PP and CSAF (only in case PP and/or CSAF differ from ITT).

5.1.2 *As planned versus as actual analysis*

For analyses done on the safety analysis set and challenge safety set, the actual treatment of the subject will be considered.

For all other analyses, the planned treatment will be used.

	Statistical Analysis Plan	
FLU010	Final analysis	Final 3.0 of 15JUN2020

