3. STUDY DESIGN

3.1 OVERVIEW OF STUDY DESIGN

This is a randomized, single-centre, double blind study. The study will screen healthy volunteers and only enrol those with MNT <20. The study consists of an outpatient vaccination phase, and at least 6 weeks later an inpatient challenge phase.

155 participants will be randomized 3:2 to receive either MVA (N=93) or Placebo (N=62) by intramuscular injection in the non-dominant arm deltoid. Vaccination-related local and systemic symptoms will be followed by participant-directed diary cards for 7 days, and unsolicited adverse events will be followed throughout the study from consent signature. The vaccinations will be administered starting in April 2019. Blood for immunogenicity and storage of samples for correlates of protection will be drawn at five time points: Days 1, 8, 28 post-vaccination, on entry to the quarantine facility for challenge (Day -1), and 27 days post-challenge (Day 28).

Up to 20 participants with no intercurrent ILI will be challenged during each of the challenge periods lasting three weeks (approximately 12 MVA-NP+M1 recipients and 8 Placebo recipients per three-week block), to achieve a total of 80 participants from the MVA-NP+M1 group and 54 from the saline Placebo group being challenged. Participants will enter the quarantine facility on Day -2 or Day -1 and be discharged the morning of Day 11. The grouping of participants undergoing challenge will be as consistent as possible with the grouping used during the randomization process; i.e., the first participants vaccinated will be the first quarantined and challenged, but in all cases at least 6 weeks will have passed between vaccination and challenge.

Participants will receive a single intranasal administration of the H3N2 challenge agent (A/Belgium/4217/2015) as a nasal spray via the Teleflex MAD301 and MAD130. The MAD301 hard plastic atomizer will be combined with the MAD130 syringe and vial adaptor to constitute components that are the most similar to the VaxINator™ kit, used in previous studies for H3N2 inoculation.

Participants will be in a semi-recumbent (45°) position, lying in bed and will receive 0.25 mL of the challenge agent solution into each nostril.

After viral inoculation, participants are to remain in a supine position for 2 hours. Participants are not allowed to blow their noses during this period. All administrations will be performed by a member of the clinical site staff.

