9. STATISTICAL METHODS

9.1 STATISTICAL ANALYSIS

No formal interim analyses are planned for this trial.

Statistical analyses will be performed by a qualified vendor under the supervision and responsibility of the Sponsor, using SAS® (SAS Institute Inc., Cary, NC, USA; version 9.2 or higher) and/or Phoenix™ WinNonlin® (Pharsight Corporation, Palo Alto, CA, USA; version 6.1 or higher). Unscheduled interim analyses may be performed at the request of the IDMC to monitor the safety of the investigative vaccine throughout the study (also Section 5.7). Details will be described in a separate IDMC charter.

The following populations will be considered for analysis:

- intent-to-treat (ITT) population, defined as all randomized participants who received the challenge inoculation, according to the assigned (randomized) treatment group

- per-protocol (PP) population, consisting of a subset of the ITT population without any major protocol deviations and including those participants who remain in the quarantine facility for the full extent of the challenge phase
- safety population, consisting of all participants vaccinated in the vaccine phase, according to the vaccination actually received
- challenge safety population, which includes all of those in the above defined ITT, according to the vaccination actually received.

Unless specified otherwise, the ITT population will be used for efficacy and immunogenicity analysis. The safety populations will be used for safety/tolerability analysis and analysis of demographics.

All statistical methods shall be detailed in a Statistical Analysis Plan (SAP) to be issued by SGS statistical team and finalized before database lock. The SAP will be approved by the Vaccitech Ltd statistical consultant.

The final efficacy analysis will be performed once all participants have completed 27 days from the time of inoculation (Day 28 post-challenge) or 6 months post-vaccination, whichever is last.

For continuous variables, descriptive statistics will include mean, standard deviation (SD), median, minimum, maximum, and range. For categorical variables, descriptive statistics will include frequencies and percentages.

9.1.1 *Baseline Characteristics*

For all participants who undergo vaccination, descriptive statistics will be provided per vaccination group for demographic (e.g. age, height, weight, BMI, race, sex) and other initial participant characteristics (physical examination, medical and surgical history, concomitant diseases).

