1.2 STUDY DESIGN

This is a randomized, single-centre, double blind study. The study screens healthy volunteers and only enrolls those with microneutralisation test (MNT) < 20. The study consists of an outpatient vaccination phase, and at least 6 weeks later an inpatient challenge phase.

155 participants are randomized 3:2 to receive either MVA-NP+M1 (N=93) or Placebo (N=62) by intramuscular injection in the non-dominant arm deltoid. Vaccination-related local and systemic symptoms are followed by participant-directed diary cards for 7 days, and unsolicited adverse events are followed throughout the study from consent signature.

A total of 80 participants from the MVA-NP+M1 group and 54 from the saline Placebo group are challenged. Participants enter the quarantine facility on Day -2 or Day -1 and are discharged on Day 11. Participants receive a single intranasal administration of the H3N2 challenge agent via nasal spray. Challenge-related local and systemic symptoms are followed up to twice a day using investigator-directed symptom score cards for 11 days.

The schedule of assessments is in section 9.4.1 for the vaccination period and in section 9.4.2 for the challenge period.

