2.2.3 Inferential statistics

The difference in background subtracted T cell response results on Day 8 and on Day 28 between MVA-NP+M1 and placebo will be analysed using an analysis of covariance (ANCOVA) model with treatment as factor, baseline as covariate and the interaction of both. Difference in LS means and corresponding 95% CI will be reported. This will be done separately for the vaccination and challenge period and for Day 8 and on Day 28. The same model will be repeated for the change from baseline in background subtracted T cell response results.

The difference in T cell response status on Day 8 and on Day 28 between MVA-NP+M1 and placebo will be analysed using a Fisher exact test.

The difference in antibody response results on Day 28 between MVA-NP+M1 and placebo will be analysed using an analysis of covariance (ANCOVA) model on the log-transformed results with treatment as factor and baseline as covariate and the interaction of both. Difference in LS means and corresponding 95% CI will be back-transformed to obtain the geometric mean ratio and corresponding 95% CI.

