14.2.4.3 T Cell Response Status (ELISpot Results) ITT
14.2.4.4 Antibody Response Actual Values Over Time ITT
14.2.4.5 Antibody Response Changes Over Time ITT

SAFETY

ADVERSE EVENTS

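### The vaccination-period T-cell comparisons leave out vaccinated participants who are not later challenged: about 13.5% at planned numbers and 22.6% in the plan's worst case

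*SAP*

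**What the plan says.** Both documents tie immunogenicity to a set defined by the challenge.

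- Protocol 9.1 has an "intent-to-treat (ITT) population, defined as all randomized participants who received the challenge inoculation", and adds: "Unless specified otherwise, the ITT population will be used for efficacy and immunogenicity analysis".
- SAP 5.1.1 defines ITT as "randomised subjects who received the challenge inoculation, according to randomised treatment group" and assigns it in the same way: "Unless stated otherwise, the ITT will be used for the efficacy and immunogenicity tables, listings and figures".

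No exception is made for the T-cell results. In SAP 8.1 the three T-cell tables carry the ITT label, for example "14.2.4.3 T Cell Response Status (ELISpot Results) ITT". So do listing 16.2.6.5 in SAP 8.2 and the T-cell figures in SAP 8.3.

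SAP 2.2.3 specifies an ANCOVA of MVA-NP+M1 against placebo on the background-subtracted T-cell response: "This will be done separately for the vaccination and challenge period and for Day 8 and on Day 28". The protocol's Period 1 schedule has PBMC samples on Days 1 (before vaccination), 8 and 28 for all vaccinated participants. SAP 1.2 expects fewer people to be challenged than vaccinated: "A total of 80 participants from the MVA-NP+M1 group and 54 from the saline Placebo group are challenged", out of 93 and 62 randomised.

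**The concern.** The vaccination-period question is what the vaccine does to T-cell responses in those randomised to it. Every vaccinated participant is scheduled to supply the data for that question before anyone in their group can be challenged. Under the ITT rule, a participant who gives Day 8 and Day 28 samples but is never challenged appears in no planned T-cell table, model, figure or listing.

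Two things are at stake. The first is precision. The second is that the comparison is no longer between the groups as randomised and vaccinated, but between those who also reached challenge. Reaching challenge can depend on what happened after vaccination: Protocol 8.2 allows withdrawal for a severe or serious adverse event, and Protocol 7.1.2.1 lets the investigator exclude for intercurrent ILI.

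The result has some weight. The protocol synopsis names ELISpot as the primary immune endpoint, and the primary hypothesis in Protocol 2.1 attributes the expected effect to T-cell induction by the vaccine.

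**Working it through.** **Inputs**
- Randomised and vaccinated: 93 + 62 = 155 (Protocol 3.1).
- Challenged, planned: 80 + 54 = 134 (SAP 1.2; Protocol Table 2 gives the surplus as 13 and 8).
- Challenged, worst case: 72 + 48 = 120 (Protocol 9.2, SAP 1.3).
- Visit windows: 7 ± 1 and 27 ± 3 days after vaccination (Protocol 7.1). Challenge: at least 6 weeks, or 42 days, after vaccination.

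**The plan's own figure.** The stated 15% over-enrolment gives 134 × 1.15 = 154.1, which agrees with 155. The exact ratio is 155/134 − 1 = 15.7%.

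**Order of events.** The latest in-window Day 28 sample falls 27 + 3 = 30 days after vaccination. The gap to the earliest challenge is 42 − 27 = 15 days at the nominal visit and 42 − 30 = 12 days at the edge of the window. Both samples precede challenge in either case.

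**Share left out** = 1 − challenged/vaccinated

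| Scenario | Vaccine | Placebo | Total |
|---|---|---|---|
| Planned | 13/93 = 14.0% | 8/62 = 12.9% | 21/155 = 13.5% |
| Worst case | 21/93 = 22.6% | 14/62 = 22.6% | 35/155 = 22.6% |

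The assumed 15–20% drop-out lies between these rows: 155 × 0.85 = 131.75 and 155 × 0.80 = 124 would remain. The sample-size section describes 72 and 48 as a 25% reduction, but 0.75 × 93 = 69.75 and 0.75 × 62 = 46.5. The stated counts are used here.

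**Relative width of the between-arm confidence interval**, with equal SD and every participant contributing = √(1/n₁ + 1/n₂) for the challenged, divided by the same for all vaccinated
- All vaccinated: √(1/93 + 1/62) = 0.1640.
- Planned: √(1/80 + 1/54) = 0.1761; ratio 1.074.
- Worst case: √(1/72 + 1/48) = 0.1863; ratio 1.137.

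**Possible bias, as an assumption only.** The documents give no figure for how unchallenged participants differ. Suppose that only those in the vaccine arm differ from their challenged counterparts, by D SD. The arm difference then shifts by (share left out) × D. For D from 0.25 to 1 this is 0.140 × D = 0.035 to 0.14 SD at planned numbers, and 0.226 × D = 0.056 to 0.226 SD in the worst case.

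**The case against.** The strongest defence is that ITT was prespecified consistently in both documents and suits most of the immunogenicity work. The listed secondary T-cell objective is correlation with vAUC, symptom scores and influenza incidence, and those outcomes exist only in challenged participants. The between-arm ELISpot comparison sits under exploratory endpoints in Protocol 9.1.2.3. One set also keeps the Day 8 and Day 28 tables on the same people as the correlation plots. This stands for the challenge-period and correlation analyses. It gives no reason to omit an all-vaccinated result for the vaccination period.

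A reader might infer that the randomised comparison is broken or biased. The documents do not support that. Planned exclusion is nearly equal by arm. Participants, adverse-event recorders, challenge staff and recruiters are blinded. A participant excluded on Day -2 may be replaced by one on the same treatment. Much of the loss may be deliberate surplus with no link to immune response. What remains is conditioning on a later event, with selection possible but undemonstrated.

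A reader might also take 13.5% as a ceiling. It is the share at full planned challenge enrolment, and Protocol 5.5 words the challenge numbers as upper figures. Nor is everyone with a positive pre-challenge PCR lost, because they may join a later cohort once cleared.

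The precision figures are a best case for the gain. Participants who leave before Day 28 add nothing at that visit, and the planned model is an ANCOVA with a baseline interaction, not a raw difference in means.

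**Conclusion.** The point holds as a limited one. The vaccination-period ELISpot comparisons condition on a challenge that comes after randomisation and after both samples, and the plan offers no all-vaccinated analysis beside them. The share left out is 13.5% by design and 22.6% at the worst-case numbers. The cost in interval width is at most about 7.4% and 13.7% respectively, if SDs are equal and samples are complete and usable. The size and direction of any selection bias cannot be derived from the documents.

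The primary endpoint is unaffected. SAP 2.2.1 drops the T-cell analyses if ELISpot results are unavailable for the final analysis, and the point then lapses. It is a worthwhile improvement, not a threat to the trial's main conclusion.

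**What to change.** In SAP 5.1.1, define a set of all randomised and vaccinated participants, analysed by randomised arm. The existing sets do not serve: SAF groups by vaccine actually received, and RND does not require vaccination. In SAP 2.2.3, 2.2.4 and 8.1–8.3, use the new set for the vaccination-period T-cell tables, models, figures and listing. Include every participant with an available ELISpot result, whether or not later challenged. Keep ITT for the challenge-period and T-cell correlation analyses. Protocol 9.1 leaves room for this, since its ITT rule applies only where nothing else is specified.

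The cost is one extra analysis set and splitting the T-cell displays by period, which SAP 2.2.4 already presents separately. No new assays are needed if only available results are used. If the laboratory did not run samples from unchallenged participants, recovering them would mean assaying up to about 21 participants' vaccination-period samples at planned numbers, or 35 in the worst case.

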5.2 PHASES AND TIME POINTS

5.2.1 *Phases*

All events and assessments will be allocated to phases.

Phase	Start	End
Screening	Date of signing the ICF, with 00:00 added as time part	Vaccination date(time) – 1 minute
Vaccination	Vaccination date(time)	Challenge date(time) – 1 minute
Challenge	Challenge date(time)	End date of Day 28 post-challenge visit, with 23:59 added as time part
Follow-up	End of challenge phase + 1 minute	Date of last contact, with 23:59 added as time part

Per definition, and for each subject, the last available phase ends on the date of last contact (or the cut-off date for the topline analysis), with 23:59 added as time part.

AEs will be allocated to phases as described in section 3.1.2. All other assessments will be allocated to phases based on the assessment date(time).

In case of (partially) missing date(time) fields which cannot be allocated to a phase based on the available date(time) information, the visit label will be used to allocate to the correct phase. If this is not possible (unscheduled visits or visits on a turning point between phases), assessments will be allocated to the vaccination phase unless the available parts of the assessments start or stop date(time) provide evidence for allocating to the challenge/screening/follow-up phase.

5.2.2 *Baseline and change from baseline*

Baseline will be defined by phase.

The vaccination baseline value is the last available and non-missing value before the first administration of any study drug and will be used for data collected during the vaccination period.

The challenge baseline value is the last available and non-missing value before the administration of challenge inoculation and will be used for data collected during the challenge period.

Change from baseline is defined as follows:

Change from baseline at time point t = value at time point t – baseline value.

	Statistical Analysis Plan	
FLU010	Final analysis	Final 3.0 of 15JUN2020

5.2.3 *Relative day*

Relative days (DY) will be calculated both with respect to the vaccination and to the challenge, according to the following rule:

- Concerned date < reference date: DY = concerned date – reference date
- Concerned date \geq reference date: DY = concerned date – reference date + 1

The reference dates are the vaccination date and the date of challenge.

5.2.4 *Analysis visits*

For vaccination and challenge assessments on or after their respective reference datetime, the analysis will use the visits and time points indicated on the subject's case report form (CRF). Unscheduled assessments on or after the reference datetime will only be listed.

The screening value is the last available and non-missing value before vaccination. Reason for this approach is the use of retest results for subject eligibility assessment.

5.2.5 *Worst-case*

A worst-case analysis visit will be created for parameters for which abnormalities and/or toxicity grades are defined to summarise values considered as the worst-case. For abnormalities it is derived per parameter and in case both the lowest and the highest values are considered abnormal, a subject can have two worst-case analysis visits for a same parameter within each phase. For toxicity grades the worst-case is the value associated to the highest toxicity grade and is derived per parameter and toxicity direction (low / high).

Worst-case will be derived within each post-screening phase, including unscheduled assessments.

